 - a. Group A patients will have sterile 2% lidocaine with Epinephrine 10 μ g/mL (Solution A1) soaked in surgical grade cotton applied to the donor site immediately after donor harvest until hemostasis is obtained according to the surgeon. If additional hemostasis is deemed necessary by the surgeon following use of 20cc (1 vial) of this Solution A1 then additional Epinephrine 10 μ g/mL will be used as per standard burn protocol. Following hemostasis, patients will have a sterile, nonpyrogenic solution of lidocaine 2% in isotonic saline (Solution A2) sprayed on the donor site of the grafted skin prior to emergence from general anesthesia. A maximum of 7mg/kg of lidocaine solution will be available for spraying. The site will then be covered with TheraBond dressing as per standard burn care used at our institution.
 - b. Group B (control group) patients will have sterile Epinephrine 10 μ g/mL solution (Solution B1) soaked in surgical grade cotton applied to the donor site immediately after donor harvest. A 20cc aliquot will be prepared in such a way as to be indistinguishable from Solution A1 by the OR team. If additional hemostasis is deemed necessary by the surgeon following use of 20cc (1 vial) of this Solution B1 then additional Epinephrine 10 μ g/mL will be used as per standard burn protocol. Following hemostasis, patients will have a control (placebo) sterile, nonpyrogenic solution of isotonic saline (Solution B2) sprayed over the donor site. The site will then be covered with TheraBond dressing as per standard burn care used at our institution.

- f) Assessment of the donor sites using the VNRS pain scores will be compared between groups in addition to the amount of narcotic pain medication required by these two groups. The amount of narcotic utilized will be analyzed per ideal body weight, per actual body weight in addition to donor site area.
- g) Lidocaine levels will be drawn at sixty minutes and six hours from application of study solution. These levels will be analyzed on a per patient and per graft size area basis to trend for systemic levels.
- h) Any adverse event occurring with the patient will be analyzed on a case-by-case basis. Wound infection rates of the donor sites at post op day 14-21 +/- 5 days will be compared between the two groups. Any adverse event deemed serious by the Principal Investigator will be submitted to the Institutional Review Board per institution policy.

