- b. Randomization procedures: Numerical randomization will be created using a computer generated numbers. Randomization envelopes will be created by research staff and maintained by the Investigational Drug Pharmacy. The Burn Study Team will alert the Investigational Drug Pharmacy to randomize each patient. The Investigational Drug Pharmacy will dispense the appropriate blinded solution for treatment. The Investigational Drug Pharmacy will dispense Lidocaine with Epinephrine or Epinephrine alone in blinded fashion for the donor site soaks. A 20cc bottle of Lidocaine with Epinephrine or Epinephrine alone will be emptied into a sterile unlabeled container prior to application of sprayed study treatment. The surgeon and OR team will remain blinded for this portion of the study. If additional hemostasis is required beyond the first study soak treatment; then the standard of care epinephrine soak will be utilized. The Investigational Drug Pharmacy will also dispense the randomized spray study treatment in an assembled applicator (LMA MADgic™) purchased for this project only. No unblinding identifiers will be on either applicators. The investigator will be blinded to all groups. Study Intervention:
 - i. Group A (Lidocaine Treatment Group): Graft site hemostasis will be obtained with 2% lidocaine and epinephrine 10 μ g/mL solution in normal saline soaked in surgical grade cotton gauze and placed over donor site for time determined by surgeon. Following hemostasis, 7mg/kg of 2% Lidocaine solution will then be sprayed on patient's donor site while under general anesthesia by burn surgeon in a sterile fashion. Upon emergence and transfer to PACU patient will be asked to rate his/her pain according to the VNRS for both donor site and overall pain. The amount of narcotics required in PACU and first 24 hours on floor will be documented. Rate of increase of narcotic requirement within the first 24 hours will also be analyzed. VNRS scores will be obtained immediately post operatively on arrival to PACU and in 24 hours.

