 - ii. Group B(Placebo Group): Graft site hemostasis will be obtained with a epinephrine 10 μ g/mL solution in normal saline soaked in surgical grade cotton gauze and placed over donor site for time determined by surgeon. Following hemostasis a control solution will be sprayed on patient's donor site while under general anesthesia by burn surgeon in a sterile fashion. Upon emergence and transfer to PACU patient will be asked to rate his/her pain according to the VNRS for both donor site and overall pain. The amount of narcotics required in PACU and first 24 hours on floor will be documented. Rate of increase of narcotic requirement within the first 24 hours will also be

analyzed. VNRS scores will be obtained immediately post operatively on arrival to PACU, 6 hours post treatment during blood draw and in 24 hours for both donor site and overall pain.

Study Table of Events

Study Assessments	Baseline	Surgical Procedure	0-24 hours post op	24-48 hours post op	Follow up (14-21 days)*
Informed Consent	X				
Inclusion/Exclusion	X				
Demographic Data	X				
Medical History	X				
Physical Exam	X				
Randomization		X			
Treatment		X			
OR Data Collection		X			
VNRS Pain Assessment			X**	X**	
Self-Reported Pain Assessment			X	X	
Wound Healing Assessment					X
Photographs		X			X

Narcotic Medication Data Collection		X	X	X	
Adverse/SAE Assessment	X	X	X	X	X
Lidocaine Level			X***		

* (+/- 5 days)

**Performed at 30 minutes after extubation, 2 hours, 6 hours and 24 hours post-op for both donor site and overall pain

***Performed at 60(+/-30 minutes) minutes and 6 hours (+/-60 minutes) post op

Safety Monitoring Plan

- a. The likelihood of adverse events in this study is very small. Lidocaine spray doses will be calculated (7mg/kg based on ideal body weight) to ensure patient is receiving safe doses. A safety analysis performed on our first 15 patients proved safety. All lidocaine levels obtained demonstrated levels significantly lower than potentially toxic dosing. We believe there could be improved pain control if more appropriate (higher) lidocaine doses are utilized. The method suggested for hemostasis with lidocaine and epinephrine is standard of care at some institutions including our own. It is regularly used by the ENT service. In addition, one of the surgeons in our study has used this method in the past.
- b. Patients will be monitored with pulse oximetry overnight per standard of care.

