Patient ID: _____ - _____

____ - ____ - ____
Date

Baseline

Physical Exam:

Vitals:			
System	Abnormal	Normal	Explanation
General			
HEENT			
Cardiovascular			
Respiratory			
Gastrointestinal			
Genitourinary			
Musculoskeletal			

Skin			
Neurologic			
Psychiatric			
Endocrine			
Heme/Lymphatic			
Allergic/Immunologic			

Patient Initials: ____-____

Page 1 of 1

Patient ID: ____-____

____-____-____
Date

Randomization

Date Randomized: ____-____-____

Time Randomized*: ____:____

Order placed in EPIC to Randomize/Dispense Study Medication:

Date: ____ / ____ / ____ Time: _____

Randomization Materials to be stored in Investigational Drug Pharmacy until study completion.

*Time dispensed on study drug/placebo packaging

Comments:

Patient Initials: ____-____**Page 1 of 1****Patient ID:** ____-____**____-____-____****Date****Surgical Procedure****Surgical Procedure Information:**

OR Date: ____ / ____ / ____ Incision Time: ____ : ____ Extubation Time: ____ :

Procedure Performed:

Area of Donor Site Harvest*: [] Left Thigh
[] Right Thigh
[] Other: _____

Donor Site Harvest Time: _____

Donor Site Dimensions: ____ cm x ____ cm = ____ cm²

Photos of Donor Sites Complete: [] Yes [] No

Time of Study Treatment Soaks:

Time ON ____ : ____ Time OFF ____ : ____

Time ON ____ : ____ Time OFF ____ : ____

Need for additional Epinephrine Soaks: [] Yes [] No

Time ON ____ : ____ Time OFF ____ : ____

Time of Study Spray Treatment: ____ : ____

Time of TheraBond Placement: ____ : ____

Post Op Admit to: [] BICU [] PACU

Post Op Admit Time: ____ : ____

* One page to be completed per donor site

Patient Initials: ____-____

Page 1 of 4

Patient ID: ____-____

____-____
Date

Post-OP Study Assessments- 30 Minutes Post Extubation

30 Minute Post-extubation VNRS Pain Assessment:

Is the subject able to provide VNRS Pain Assessment related to donor site pain only:

[] Yes [] No

Time: ____ : ____ Score : ____

Is the subject able to provide VNRS Pain Assessment related to overall pain:

[] Yes [] No

Time: ____ : ____ Score : ____

VNRS Pain Assessment recorded by: _____

Comment: [] Yes [] No

Post-OP Study Assessments- 60 Minutes (+/- 30 minutes)

60 Minute Post-op Lidocaine Level:

Lidocaine Level Drawn By: [] Shands Lab Phlebotomy [] Research Staff

Time of Lab Draw: ____ : ____ Result: ____ mcg/mL **Normal Range 1.5-5.0 mcg/mL**

Lidocaine Level added to Participant Tracking Log: [] Yes [] No

Comment: Yes No

Patient Initials: _____

Page 2 of 4

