Patient ID: _____ - _____

_____ - _____
Date

Post-OP Study Assessments- 2 Hours

2 Hour Post-op VNRS Pain Assessment:

Is the subject able to provide VNRS Pain Assessment related to donor site pain only:

Yes No

Time: ____: ____ Score : _____

Is the subject able to provide VNRS Pain Assessment related to overall pain:

Yes No

Time: ____: ____ Score : _____

VNRS Pain Assessment recorded by: _____

Comment: Yes No

Post-OP Study Assessments- 6-Hours (+/-60 minutes)

6 Hour Post-op Lidocaine Level:

Lidocaine Level Drawn By: Shands Lab Phlebotomy Research Staff

Time of Lab Draw: ____:____ Result: _____ mcg/mL **Normal Range 1.5-5.0 mcg/mL**

Lidocaine Level added to Participant Tracking Log: Yes No

Comment: Yes No

For more information, contact the Office of the Vice President for Research and Economic Development at [contact] or [contact].

Patient Initials:

Page 3 of 4

Patient ID: -

Post-OP Study Assessments- 6 Hours

6 Hour Post-op VNRS Pain Assessment:

Is the subject able to provide VNRS Pain Assessment related to donor site pain only:

[] Yes [] No

Time: ____ : ____ Score : _____

Is the subject able to provide VNRS Pain Assessment related to overall pain:

[] Yes [] No

Time: ____ : ____ Score : _____

VNRS Pain Assessment recorded by: _____

Comment: Yes No

Comments:

Patient Initials:

Page 4 of 4

Patient ID: -

Date

Post-OP Study Assessments- 24-Hours

24 Hour Post-op VNRS Pain Assessment:

Is the subject able to provide VNRS Pain Assessment related to donor site pain only:

[] Yes [] No

Time: ____ : ____ Score : _____

Is the subject able to provide VNRS Pain Assessment related to overall pain:

[] Yes [] No

Time: ____ : ____ Score : _____

VNRS Pain Assessment recorded by: _____

Comment: Yes No

Comments:

Patient Initials:

Page 1 of 1

Patient ID: -

— · — · —

Date

Follow-Up Assessment- 14-21 Days Post-op (+/- 5 days)

Follow-Up Assessment:

Date of follow-up appointment: ____ / ____ / ____

Has there been any infections to the Study Donor Site area?

[] Yes [] No

Has the Therabond been completely removed from the Study Donor Site?

[] Yes [] No

Is the donor site 100% healed? [] Yes [] No : _____ % healed

Current Treatment for Study Donor Site: _____

Photographs taken of Study Donor Site? [] Yes [] No

Photographs taken of Study Donor Site? [] Yes

Comments:

Patient Initials:

Page 1 of ____

Patient ID: ____-____ **ADVERSE EVENTS**

Adverse Event # ____

AE Start Date: ____ / ____ / ____

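### The lidocaine results go on the same post-operative form as the pain scores and on a tracking log, and no rule keeps them from the people who assess outcomes, so the stated blinding is not protected after surgery

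*Combined protocol and SAP*

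**What the plan says.** Section 6 (Research Plan, Study Design a) calls the trial double-blind, and Study Procedures b (Randomization procedures) adds: "The investigator will be blinded to all groups".

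The measures behind that statement concern the product:
- For the control soak, Study Design e.b says "A 20cc aliquot will be prepared in such a way as to be indistinguishable from Solution A1 by the OR team".
- For the spray, Study Procedures b says "No unblinding identifiers will be on either applicators".
- The pharmacy dispenses both, and the soak is poured into an unlabeled container.

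Group B has an epinephrine soak, after which "patients will have a control (placebo) sterile, nonpyrogenic solution of isotonic saline (Solution B2) sprayed over the donor site".

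Lidocaine is measured twice after surgery. The post-operative pages of Appendix C have a result line for the 60-minute level and another under "6 Hour Post-op Lidocaine Level". Each is printed with "Normal Range 1.5-5.0 mcg/mL" and a tick box reading "Lidocaine Level added to Participant Tracking Log". Either the hospital phlebotomy service or research staff may draw the sample. The Group B text (Study Procedures b.ii) schedules pain scores "6 hours post treatment during blood draw and in 24 hours for both donor site and overall pain", so controls are sampled too.

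Appendix A assigns the scheduled Verbal Numerical Rating Scale (VNRS) scores to research staff. Study Design c adds scores taken by hospital staff. Study Design i has the burn research team judge donor-site healing by eye. Safety Monitoring Plan f has every investigator take part in interpreting the second safety analysis.

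**The concern.** A drug level in a placebo-controlled trial can reveal the arm as surely as a label on the vial. Here the plan masks the vial and says nothing about the level. If someone who elicits a pain score or judges healing has seen a measurable level, that assessment is no longer blind, and a reader of the results could not verify that it was.

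Two outcomes matter most. The 24-hour VNRS comes well after both draws. The healing assessment is the team's own visual judgment, and it addresses the worry, raised in the Background, that lidocaine might interfere with healing.

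**Working it through.** The plan gives no figure of its own on this point. The check sets the passages side by side and works out the timing.

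**1. Does a level carry information about the arm?** Group A receives lidocaine in both soak and spray. Group B receives it in neither, and the anaesthetic regimen in Study Design c names no other lidocaine. The Background cites a study of lidocaine sprayed on donor sites at up to 6.7 mg/kg: average peak 1.4, maximum 2.2 (units not printed), still detectable at 6 hours. A measurable level therefore points to Group A. The converse is weaker. The assay's detection limit is not given, and the 1.5 mcg/mL at the foot of the printed range is not one. Not every Group A patient need be identifiable.

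**2. Where do the results sit relative to the scores?** In the four-page post-operative set of Appendix C:
- page 1: 30-minute VNRS and 60-minute level
- page 2: 2-hour VNRS and 6-hour level
- page 3: 6-hour VNRS
- page 4: 24-hour VNRS

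The follow-up form is separate and has no lidocaine field.

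**3. Is there a withholding rule?** None appears in the Randomization procedures, Safety Monitoring Plan, Analysis Plan, Appendix A or Appendix C. The Safety Monitoring Plan reports that levels from a safety analysis of the first 15 patients were examined, so levels are looked at while the trial runs. Whether they carried patient identifiers is not stated.

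**4. Timing on a post-operative clock** (Study Table of Events; extubation is taken as time zero, an assumption). Draw 1 is at 1 ± 0.5 h, so 0.5 to 1.5 h. Draw 2 is at 6 ± 1 h, so 5 to 7 h. Gap = score time minus draw time:
- 2-hour score: 2 − 1.5 = 0.5 h to 2 − 0.5 = 1.5 h after draw 1
- 6-hour score: 6 − 1.5 = 4.5 h to 6 − 0.5 = 5.5 h after draw 1; from 1 h before to 1 h after draw 2
- 24-hour score: 24 − 1.5 = 22.5 h to 24 − 0.5 = 23.5 h after draw 1; 24 − 7 = 17 h to 24 − 5 = 19 h after draw 2
- healing visit: earliest day 14 − 5 = 9, latest day 21 + 5 = 26; 9 × 24 − 7 = 209 h, or 8.7 days, after the latest draw 2

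A score is exposed only if the result returned within its gap and the scorer saw it.

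**5. Timing from application.** Study Design g times the draws from application of the study solution, which precedes emergence. Let E be the hours from application to extubation (not given). Draw 1 then falls 1 − E hours after extubation, which is at or before the 30-minute score whenever E ≥ 0.5. If the ±30-minute window is carried over, the earliest draw is at 0.5 − E, before that score for any E > 0. The 24-hour gaps become 22.5 + E to 23.5 + E and 17 + E to 19 + E, longer than on the first clock.

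**The case against.** The strongest reply is that the documents show a silence, not a leak. The protocol commits to a blinded investigator. The tracking log is not reproduced, so nobody can say who reads it. Turnaround and the moment at which the result line is filled in are not stated. Drawing a sample is not seeing its result, phlebotomy may draw it, and a score taken at the 6-hour draw cannot be influenced by that draw's result. All of this stands, and it limits the point to possible unblinding. It does not remove the point: the form puts the results in the same set as the scores, and nothing offsets that.

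The reply on outcomes also has force. The VNRS is the patient's own rating, so any bias through the person eliciting it is indirect. Hospital-staff pain scores, days to dressing removal and photographs are also collected. The Analysis Plan names no healing test. If its pain comparison uses donor-site minus overall pain, a bias common to both would largely cancel.

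A reader might infer more than the documents support:
- **That assessors were unblinded.** No passage shows anyone seeing a level before scoring.
- **That product masking is complete and only the levels are at fault.** Indistinguishability is written for the soak. For the spray, the text says only that applicators carry no identifiers.
- **That the 30-minute score is safe.** This holds only on the post-operative clock (step 5).
- **That the forms themselves expose the healing assessment.** They do not. Exposure would have to come through the log, shared personnel or the safety review.
- **That the false-positive rate rises by some stated amount.** The documents give no basis for the size of an assessor effect or the fraction of patients identified.

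**Conclusion.** The point holds as a gap in protection. Masking is specified for the product, results that can reveal the arm are recorded alongside the pain scores and on a log, and no rule keeps them from outcome assessors. Completing the forms as printed can therefore work against the blinding statement.

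The 24-hour VNRS is the clearest case: it follows both draws on either clock, by at least 17 hours. Exposure of earlier scores depends on turnaround and on which clock applies, so none should be declared unexposed. The healing visit is at least 8.7 days after the last draw, but its exposure needs a route other than the follow-up form. The size of any bias is unknown, and no effect on as-needed opioid use is shown.

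The conclusion assumes that Group B has no other source of lidocaine and that at least some Group A levels are measurable. Confidence is high about the missing rule and limited about actual exposure. This is a cheap improvement worth making.

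**What to change.** 1. On the form used by pain assessors, replace the result line and the tracking-log line with the draw time and a tick that the sample was sent.
2. Send results to the Investigational Drug Pharmacy, or to another existing person outside outcome assessment. Keep a defined safety route to the treating physician, and for assessing adverse events, since the Principal Investigator judges their seriousness.
3. Merge the levels for the per-patient and per-graft-area analysis in Study Design g after database lock.
4. At the second safety analysis, show levels without patient identifiers to anyone who assesses outcomes.

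The cost is a form edit, a routing instruction and some coordination with the laboratory. If results post to the hospital record, a display restriction or coded sample label is also needed. The downside is that investigators no longer see individual levels routinely in real time, which is why the safety route must be written down. The change cannot help patients already assessed. The first 15, whose safety analysis is reported, had already been treated.

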Project Title:

LIDOCAINE IN THE TREATMENT OF POST-OPERATIVE PAIN
MANAGEMENT FROM A DONOR SITE AFTER SPLIT THICKNES SKIN GRAFT
HARVESTING FOLLOWING BURN INJURY OR WOUND TREATMENTS

NCT #:

NCT02229578

Document date:

December 08, 2016

Protocol

1. Project Title:

LIDOCAINE IN THE TREATMENT OF POST-OPERATIVE PAIN MANAGEMENT FROM A DONOR SITE AFTER SPLIT THICKNESS SKIN GRAFT HARVESTING FOLLOWING BURN INJURY OR WOUND TREATMENTS

2. Investigator(s): **[name]**

[name]

[name]

[name], ARNP

[name]

3. Abstract:

Burn pain is known to be one the most severe forms of acute pain often requiring large amounts of narcotics in addition to other adjuvants. Wounds can also cause a great deal of pain in this population. Topical lidocaine is effective for controlling pain in various settings including dressing changes of burns. The aim of this study is to demonstrate the effectiveness of topical lidocaine in decreasing pain scores and narcotic requirements when applied to donor graft sites while at the same time not interfering with the standard of care TheraBond dressing. During this study we will be monitoring for evidence of delayed wound healing, and surgical site infection.

4. Background:

Pain from burns is a severe form of acute pain that requires aggressive use of opioids.¹ Even with the implementation of multiple modalities for analgesia, pain from skin debridements and grafting procedures remains a challenge to control.^{2,3} Local anesthetics have been used for pain relief in burn patients previously as a topical gel or IV infusion and have been found to significantly reduce medication consumption, without apparent adverse effects on wound healing.^{2,4,5} Lidocaine actually has potent anti-inflammatory effects which could be advantageous on wounds.¹ In addition, topical application of lidocaine to wounds result in different degrees of systemic absorption. High concentrations of lidocaine have potential for central nervous system (seizures ($>5\text{mg/L}$)) and cardiovascular toxicity (arrhythmias ($>9\text{mg/L}$)).⁴ Plasma concentration of lidocaine depend upon drug dose, rate of absorption, patient weight, physical status and thickness of skin harvested.⁶ A prior study where up to 6.7mg/kg of 2% lidocaine with epinephrine was sprayed on donor

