- c) Consent will be obtained from non-intubated patients willing to participate in the study that are admitted to the Burn Service for treatment of their burn or wound. All patients will undergo general anesthesia. Standard induction will be performed with Fentanyl and Propofol. Maintenance will primarily be with the volatile agent sevoflurane. Acetaminophen 1g IV and Ketorolac 30mg IV will be administered for baseline pain control intraoperative within the last 30 minutes prior to extubation. Fentanyl, Hydromorphone or Morphine will be

titrated in at end of the case as part of standard management. Hydromorphone, as needed (PRN), orders will be written for pain control in the recovery room as well as one time dose of Oxycodone 5-15mg PO. If patient requires more than 2mg of Hydromorphone then subsequent pain will be treated with Ketamine IV (10mg every 15 minutes up to 50mg total) and 1-2mg of IV midazolam. If pain is still not adequately controlled patient will be treated with an additional 2mg of Hydromorphone IV and Hydromorphone PCA will be initiated. Once discharged from the PACU to the surgical floor the patient will have PRN Oxycodone PO every 4 hours and/or Hydromorphone PO every 4 hours in addition to PRN Hydromorphone 0.2-0.5mg available. If pain control is still not adequate patient will be started on Hydromorphone PCA. The amount of hydromorphone required in PACU and in the first 24 hours following surgery will be compared between the two groups as well as self-reported donor site and overall pain according to the Verbal Numerical Rating Scale (VNRS) obtained from the patient by Research staff and by the hospital staff per standard of care.

- d) Lidocaine 2% with Epinephrine 10 μ g/mL will be placed on the donor site immediately following harvesting until hemostasis has been obtained per the surgeon. The total of up to 7mg/kg, as recommended by leading anesthesia textbooks, of lidocaine solution will also be sprayed onto the patient's donor site based on patient's ideal weight (BMI 25 or actual patient's weight if BMI <25).¹⁰
- e) 50 patients split into two (study & control) groups.

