- c. All patients enrolled in the study will have risks and benefits thoroughly explained to them.
- d. Any adverse events will be well documented and thoroughly investigated. Seriousness of event will be assessed by the Principal Investigator. All events deemed serious will be submitted to the University of Florida Institutional Review Board in accordance with institutional policy.
- e. Dressing site will be evaluated daily per standard of care by the burn team until hospital discharge.
- f. After 10 additional evaluable patients, have been enrolled a second safety analysis will be performed; all investigators will be involved in data interpretation.

Analysis Plan

An independent groups t-test (Student's t-test) will be performed to compare the mean rating between the difference of the two reported pain scale ratings. Each patient will be used as his/her own control by comparing the amount of narcotics utilized prior to surgery. An alpha level of 0.05 and power of 0.8 will be used to address the difference in the two groups. Given the desired alpha the sample size was estimated by pre-determined tables for certain values, by Mead's resource equation. With an effect size (Cohen's d) of 0.8 it is estimated that 25 patients in each

group will be needed in order to show statistical significance. An interim analysis will be conducted at 10 patients in each group and significance will be analyzed.

The amount of hydromorphone utilized in the PACU immediately post op and within the first 24 hours will be compared between the two groups and trended within the same group. Once again, an independent groups t-test will be performed to compare the mean quantity of hydromorphone required between the two groups. An alpha level of 0.05 and power of 0.8 will be used to address the difference in the two groups.

7. Possible Discomforts and Risks:

The patient's regular medical care will not change because they are enrolled in this study.

Possible risks to you may include:

- The risks from skin grafting and donor site include those associated with any surgical procedure that involves general anesthesia. These include reactions to the anesthesia, medications, nausea, pain, problems breathing, excessive bleeding, and infection.

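### The single pain test in the Analysis Plan is not tied to a rating, time or source, although eight research-staff VNRS scores per patient are scheduled, so the claim of lower pain has no defined error rate.

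*Combined protocol and SAP*

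**What the plan says.** The Abstract sets a confirmatory aim, to "demonstrate the effectiveness of topical lidocaine in decreasing pain scores and narcotic requirements".

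For pain, the Analysis Plan names one independent-groups t-test, which is to "compare the mean rating between the difference of the two reported pain scale ratings". It adds: "An alpha level of 0.05 and power of 0.8 will be used to address the difference in the two groups". The sample size is 25 per group at Cohen's d of 0.8.

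Other sections describe more pain data than one test can use:

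- The footnote to the Study Table of Events says of the VNRS: "Performed at 30 minutes after extubation, 2 hours, 6 hours and 24 hours post-op for both donor site and overall pain". Appendix A repeats this schedule for research staff, and the case report forms have a field for each of the eight scores.
- Study Design c) says the groups will be compared on "self-reported donor site and overall pain according to the Verbal Numerical Rating Scale (VNRS) obtained from the patient by Research staff", and also on scores taken by hospital staff. Appendix A adds the pain scores charted in EPIC over the first 24 hours.
- Study Design f) mentions the donor site only and gives no time: "Assessment of the donor sites using the VNRS pain scores will be compared between groups".
- The Study Intervention text gives other schedules: PACU arrival and 24 hours for Group A; PACU arrival, 6 hours and 24 hours for Group B.

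No section names a primary pain score, a summary over time, an order of testing or a multiplicity adjustment.

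**The concern.** A test controls error only if its variable is fixed before the data are seen. Here the test is named and its variable is not. The two ratings could be donor site and overall pain, or two time points, and the score could come from research staff or from the chart. The choice matters because the candidates measure different things. The solution goes only on the donor site, while overall pain also includes the grafted burn or wound. It is also given once, so a score at 30 minutes and a score at 24 hours ask different questions.

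At stake is whether a significant pain result can be read as evidence at the stated level. Settling how pain and hydromorphone share alpha would not cure this, because pain itself would still be undefined.

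**Working it through.** **Inputs.** From the Analysis Plan: alpha 0.05, power 0.8, d = 0.8, 25 per group. From the Study Table of Events and Appendix A: 2 ratings × 4 times = 8 research-staff scores. Sidedness is not stated. The documents give no correlation between scores, so a range is assumed.

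**Step 1: the plan's own figure.** Normal approximation, two-sided:

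n per group = 2 × ((1.960 + 0.842) / 0.8)² = 24.5, rounded up to 25.

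This reproduces the plan's 25. A one-sided test would need 20, so two-sided 0.05 is inferred. Exact t power at 25 per group is 0.79.

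**Step 2: chance of a false positive if any of the eight scores may carry the claim.** With independent scores the rate is 1 − 0.95⁸ = 0.337 in either direction. For lower pain only, at 0.025 per test, it is 1 − 0.975⁸ = 0.183. Scores from one patient are correlated, so null trials were simulated: 25 per arm, eight normal outcomes with a common correlation, a two-sided t-test at 0.05 on each.

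| Assumed correlation | Any significant result, either direction | Any significant result for lower pain |
|---|---|---|
| 0.3 | 0.30 | 0.15 |
| 0.5 | 0.25 | 0.13 |
| 0.7 | 0.19 | 0.10 |
| 0.9 | 0.12 | 0.06 |
| One prespecified contrast | 0.05 | 0.025 |

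In both columns the inflation is roughly 2.4 to 6 times nominal. A site-by-time structure (0.7 between ratings, 0.5 between times) gives 0.25 and 0.13, close to the row for 0.5. The EPIC scores are not counted.

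**Step 3: possible remedies, power at 25 per group.**

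- Bonferroni over eight tests (alpha 0.05 / 8 = 0.00625): 0.49 at d = 0.8.
- One named time at d = 0.8: 0.79.
- Mean of the 30-minute, 2-hour and 6-hour donor-site scores: the effective size is d_eff = mean(d) / √((1 + 2ρ)/3). At ρ = 0.5 the divisor is √(2/3) = 0.816.

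| Effect at 30 min / 2 h / 6 h | d_eff at ρ = 0.5 | Power |
|---|---|---|
| 0.8 / 0.8 / 0.8 | 0.800 / 0.816 = 0.98 | 0.92 |
| 0.8 / 0.8 / 0.4 | 0.667 / 0.816 = 0.82 | 0.81 |
| 0.8 / 0.4 / 0.2 | 0.467 / 0.816 = 0.57 | 0.51 |
| 0.8 / 0 / 0 | 0.267 / 0.816 = 0.33 | 0.20 |

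With a constant effect, power of the mean is 0.97 at ρ = 0.3 and 0.87 at ρ = 0.7.

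**Step 4: the interim look.** The Analysis Plan tests significance at 10 per group with no adjustment. For a single contrast tested at 5% at 10 and at 25 per group, simulation gives about 8.6% two-sided. The rates in Step 2 exclude this.

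**The case against.** The strongest reply is that the Analysis Plan names one pain test, not eight. The eight scores are a collection schedule, and no section says that each will be tested or that any one of them would suffice. That stands, and it makes the rates in Step 2 conditional. It does not remove the defect: Study Design c) says both ratings from both sources will be compared between groups, and the one named test can be read in several ways.

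A reader might infer that a claim of lower pain carries a false-positive rate of about 25% instead of 5%. The documents do not support that. The 25% requires an assumed correlation near 0.5, and it counts results in either direction, including more pain with lidocaine. At that correlation the matching figure for lower pain is about 13%, against 2.5%.

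It is also fair to say that any one prespecified rating and time would restore control. A mean over early scores is one option, and Step 3 shows that it loses power if the effect fades quickly. The Background reports that lidocaine was still detectable at 6 hours in a cited study; it does not say when sampling ended, so it cannot settle which window is best.

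**Conclusion.** The point holds as a failure to identify the deciding pain contrast. If any of the eight scheduled scores could support the claim, the chance of at least one false significant result is about 12% to 30% in either direction, or about 6% to 15% for lower pain against 2.5%. This assumes two-sided 5% tests, 25 per arm, approximately normal scores and a common correlation between 0.9 and 0.3, before the interim look. The absence of a fixed rating, time and source is plain from the documents; the size of the inflation rests on these assumptions. It should be corrected, because as written a positive pain result could not be assigned an error rate.

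**What to change.** Before unblinding, replace the pain sentence in the Analysis Plan with one confirmatory contrast: the between-group difference in research-staff donor-site VNRS, at one named time or as one summary, for example each patient's mean over 30 minutes, 2 hours and 6 hours. State that the test is two-sided. The new sentence should drop the difference wording, or define it if a difference is really intended. Label all other times, all overall-pain scores and the EPIC scores secondary or exploratory, reported with 95% confidence intervals and no claim of effectiveness.

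Reconcile the VNRS schedules in the Group A text (two times), the Group B text (three) and the table footnote and Appendix A (four), so that both groups are measured at the same times. The chosen contrast must use times that this schedule contains. Alpha for the interim look needs its own rule; naming one contrast does not supply it.

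The cost is a few sentences, with no new data or patients. Two things are given up. A result at another time, or on overall pain alone, no longer counts as demonstrating effectiveness. A mean beats a single time only if the effect lasts, so the choice should follow the duration of effect that the investigators expect.
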